9.10 Pregnancy Reporting

If the patient or partner of a patient participating in the study becomes pregnant during the 18-week study, the Investigator should report the pregnancy to the IRB within 24 hours of being notified. The IRB will then forward the exposure in-utero form to the investigator for completion.

If a patient becomes pregnant while in the study, their medical care will be customized in discussion with the trial PIs. Safety and monitoring procedures will continue to be performed. The major concern is the known teratogenic effect of high-dose fluconazole in the first trimester.

The patient should be followed by the investigator until completion of the pregnancy. If the pregnancy ends for any reason before the anticipated date, the investigator should notify the IRB. At the completion of the pregnancy, the investigator will document the outcome of the pregnancy. If the outcome of the pregnancy meets the criteria for immediate classification as an SAE (i.e., postpartum complication, spontaneous abortion, stillbirth, neonatal death, or congenital anomaly), the investigator should follow the procedures for reporting an SAE.

9.11 Expedited Reporting

During the AE reporting period of 2 weeks to comply with national regulations, reports of all suspected unexpected serious adverse reactions (SUSARs) will be submitted to the IRB with oversight within 7 calendar days of the study site awareness of the AE. Relevant follow-up information will subsequently be communicated within 8 days.

Reporting will be via the 'Adverse Event Reporting CRF.' Copies of each report and documentation of IRB notification and receipt will be kept in the Clinical Investigator's binder.

All other suspected unexpected serious adverse reactions will be reported to the FDA, applicable competent authorities and Ethics Committees as required as soon as possible but within a maximum of 15 days of first knowledge by the Sponsor. Relevant follow-up information will subsequently be communicated within 15 days.

The Sponsor will also inform all investigators as required.

Listings of SAEs related to 5FC will be included in the Development Safety Update Report.

At the time of the initial report, the following information will be provided:

• Study identifier	• A description of the event
• Study Site	• Medical treatments given/discontinued
• Subject number	• Working diagnosis
• Date of event	• Current vital status

Within the 7 calendar days following the event, the investigator will provide further information in the form of a written narrative. This will be documented along with any other diagnostic information that will assist the understanding of the event. Significant new information on ongoing SAEs will be provided promptly to the study sponsor and local IRB of record.

Any health authority safety reports will also be submitted to the Uganda National Drug Authority, both expedited and on an annual basis.

10. CLINICAL MONITORING

10.1 Site Monitoring Plan

Site monitoring will be conducted to ensure that the human subject protection, study procedures, laboratory, study intervention administration, and data collection processes are of high quality and meet the sponsor, ICH E6 and regulatory guidelines. The objectives of a monitoring visit are to:

- Verify the existence of signed informed consent documents and documentation of the Informed Consent Form process for each monitored subject;
- Verify the prompt and accurate recording of all monitored data points, and prompt reporting of all SAEs;
- Compare data abstracts with individual participants' records and source documents (laboratory analyses and test results, and any other relevant original subject information);
- Help ensure investigators are in compliance with the protocol.

10.2 Medical Monitor

The medical monitor will review the overall clinical progress of the study and provide protocol guidance and clarifications as needed. The medical monitor will review AE CRFs for the appropriateness of: working/final diagnoses, SAE designation, AE severity grade,

expectedness, and relatedness to study medication. The medical monitor will provide feedback to the study investigators, requesting further documentation, as needed.

10.3 Data and Safety Monitoring Board (DSMB) Safety Reviews

Refer to the DSMB Charter for full details.

- DSMB safety reviews will occur after 10 participants have been enrolled and have accrued approximately 2 weeks of follow-up data.

The DSMB committee will consist of [name] as the chairperson, [name], [name], [name], and [name]. The trial PIs and statistician will present to the DSMB in an open session before the DSMB enters into a closed, private session. A quorum of three members will be required to meet, including the DSMB statistician. A local Ugandan community member will be invited to attend open DSMB meetings. The PhD study biostatistician will prepare summary progress reports on tolerability, safety, and efficacy within approximately 30 days of 10 participants being enrolled and accruing 2 weeks of follow up data. At time of the safety reviews, all available data will be utilized, particularly with respect to control subjects.

Data are unblinded, thus the PI, on-site investigators, and other team members will additionally monitor for any unexpected concern. If concerns are raised, this will prompt an unscheduled DSMB safety evaluation.

If there are unexpected safety concerns of serious and potentially related AEs, these AEs will be reviewed by the DSMB, and reported to the relevant regulatory authorities with oversight. Unexpected safety concerns may result in suspension of further trial interventions or closure to further enrollment. The study PIs, DSMB chair, and sponsor each retain the authority to suspend additional enrollment and study interventions for the entire study; however, consensus agreement will be sought. Examples of findings that might trigger a safety review are the number of SAEs overall, the number of occurrences of a particular type of SAE, severe AEs/reactions, or increased frequency of events. In particular, the investigators will be monitoring for culture positive Cryptococcal relapse. This has been rare in previous trials and a small number of cases would be cause for an early safety review. The biostatistician will perform a formal analysis as per the statistical plan.

Reporting to the IRB of record will occur with annual reporting, and after each DSMB report. We will report all deaths, including cryptococcal related deaths to the IRB.

11. STATISTICAL CONSIDERATIONS

11.1 Statistical Analysis Plan

Descriptive statistical methods will be used to summarize the data from this study, with hypothesis testing performed for the primary efficacy endpoint. Unless stated otherwise, the term "descriptive statistics" refers to number of subjects (N), mean, median, standard deviation,

standard error, minimum, and maximum for continuous data and frequencies and percentages for categorical data. All data collected during the study will be included in data listings. Unless otherwise noted, the data will be sorted first by treatment assignment, subject number, and then by date. Unless specified otherwise, all statistical testing will be two-sided and will be performed using a significance (alpha) level of 0.05. The statistical analyses will be conducted with the SAS® software package version 9.4 or higher or R Studio® 2022.07.1 or higher. All analyses will be subject to formal verification procedures. Analysis will be by intent-to-treat principle.

11.2 Timing of Analyses

The primary analysis of the primary and key secondary endpoints will be conducted once the last patient completes 2 weeks of the study or discontinues prematurely, and the resulting database is cleaned and locked.

A follow-up analysis will be conducted including all data through Week 18 once the last patient completes 18 weeks on study or discontinues prematurely.

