Phase II Study Drug and Dosing	
 • Participants will receive 5-FC 60mg/kg/day for 10 days. • Participants will receive IV AMB 0.7-1.0 mg/kg/day for 7 days. • Liposomal Amphotericin B single IV dose 10 mg/kg is preferred, when available. • All participants will receive fluconazole 1200 mg/day during consolidation therapy from day 1 to 14 then 800 mg/day from day 15 to 10 weeks, and 200mg/day after 10 weeks.
Phase II Monitoring	
 • All participants will have CSF quantitative fungal cultures performed on Days 1, 2-4, 5-7, and 10-14 of antifungal treatment. • 3x weekly CBC, chemistries, and kidney function tests for duration of induction therapy during hospitalization
Phase II Safety Analysis	
The Data Monitoring Committee (DMC) will conduct interim safety analysis after 10 participants are enrolled with >2 weeks of accrued data and calculable EFA.
 
EFA and culture positive Cryptococcus relapse will be monitored by the trial investigators, and if statistical evidence shows that EFA <0.2 log₁₀ CFU/mL/day, then an early DMC will be called.

Phase II Statistical Design Rationale	
Early fungicidal activity (EFA) is a quantitative measure of antimicrobial activity for an antifungal regimen in human patients with cryptococcal meningitis. In numerous trials, EFA correlates well with 10-week mortality. Specifically, EFAs worse than 0.20 log₁₀ CFU/mL/day are associated with higher mortality (>50%) and EFA better than 0.3 log₁₀ CFU/mL/day is associated with lower mortality (30-40%).
 
EFA is calculated by measuring the slope of the clearance rate of yeast from CSF, which is calculated from longitudinal quantitative CSF cultures collected over two weeks.
 
By intent to treat analysis, all participants who are enrolled in this study will be included for analysis.

Clinical Trial Sites	
 1. Mulago Hospital, Kampala, Uganda 2. Kiruddu Hospital, Kampala, Uganda 3. Mbarara Regional Referral Hospital, Mbarara, Uganda

Estimated Time to Complete Enrollment:	Up to 12 months
---	-----------------

Table of Contents

1. KEY ROLES	1
2. BACKGROUND AND SCIENTIFIC RATIONALE	2
2.1 Background Summary and Study Hypotheses	2
2.2 Burden of Cryptococcal Meningitis	2
2.3 Treatment of Cryptococcal Meningitis	4
2.4 Rationale for Optimizing 5FC Dose	6
2.5 Early Fungicidal Activity	7
2.6 Potential Risks and Benefits	10
3. OBJECTIVES	12
3.1 Study Objectives	12

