2.2 Burden of Cryptococcal Meningitis

Cryptococcal meningitis has become the most common cause of adult meningitis in many parts of Africa,¹³ where cryptococcosis now rivals tuberculosis in all-cause mortality.¹⁴ While long-term survival has improved with widespread use of antiretroviral therapy in high-income countries, early mortality remains high.¹⁵ Furthermore, expanding access to antiretroviral therapy in resource-limited

settings has not yet led to compelling improvements in mortality, with 10-week mortality rates between 24% and 37%, even under optimal research conditions.^{16,17} Early mortality rates are often ~70% in routine practice where access to diagnostics or medications is limited or unavailable, intracranial pressure is uncontrolled, or in settings where other barriers to the management of cryptococcal meningitis exist.^{18–20} Intravenous administration of amphotericin B deoxycholate is not often possible in resource-limited settings, even when it is available.

Even with amphotericin-based induction therapy, survival is not optimal. Figure 2.2 displays the survival in Uganda from 2013-2017 in the setting of a study using IV amphotericin + fluconazole induction therapy and control of intracranial pressure.^{21,22} Approximately, half of the mortality occurs during the first two weeks and the other half during the next 18 weeks, particularly in the first 6 weeks (Figure 2.2). This 18-week time period captures 95% of the 5-year mortality in Uganda.²³

Figure 2.2: Survival After Cryptococcal Meningitis by Glasgow Coma Scale (GCS) in Uganda

GCS < 15 = altered mental status, GCS = 15 = intact mental status, responsive to voice

The efficacy and safety of induction therapy for cryptococcal meningitis can be evaluated effectively with all-cause mortality as an early clinical outcome. This is because approximately half of the mortality related to CM occurs during the first two weeks.²⁴ 18-week outcomes will also be assessed for further evaluation of primary and secondary endpoints.

Table 2.2: The 2-week mortality of Ugandans on Amphotericin + Flucytosine with GCS=15

Study	Number of Patients	Number Died	2-week Mortality	95% Confidence Interval
EnACT Stage 1-3	25	1	4.00%	-3.7%, 11.7%

Jarvis et al. NEJM 2022; Uganda GCS=15 data	197	17	8.60%	4.7%, 12.6%
Average	222	18	8.10%	4.5%, 11.7%

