4. STUDY DESIGN

4.1 Phase II Study Design

Figure 4.1

This is a single-arm trial with historical controls to compare the efficacy and safety of reduced dosing of 5-FC induction therapy for the treatment of cryptococcal meningitis in combination with IV AMB to standard of care, with EFA as the primary endpoint.

Participants will be enrolled into an investigational cohort at study entry.

1. The investigational cohort will receive 60mg/kg/day of 5-FC divided into 3 doses per day for 10 days, n~50 total enrolled to achieve n=36 CSF culture positive.
2. The control group will consist of historical participants in the AMBITION trial
3. All participants will receive liposomal Amphotericin B 10 mg/kg, single-dose infusion, if available.
4. If liposomal Amphotericin is unavailable, participants will receive IV amphotericin deoxycholate 0.7-1.0 mg/kg/day for 7 days.
5. All participants will receive fluconazole 1200 mg/day during induction therapy from day 1 to 14 then consolidation therapy 800 mg/day from day 15 to 10 weeks, and maintenance therapy of 200 mg/day after 10 weeks.
6. All participants will receive lumbar punctures at diagnosis, day 3, day 5-7, day 10-14, and additionally as required for control of intracranial pressure and documentation of CSF sterilization. Therapeutic LPs conducted during the first week have a ~70% relative survival benefit.

Investigational cohort will receive:

- IV Amphotericin B deoxycholate 1 mg/kg/day for 7 days or IV Liposomal Amphotericin B 10mg/kg single dose.
- Oral flucytosine (5FC) 60mg/kg/day for 10 days in 3 divided doses
- Oral fluconazole 1200mg/day from Day 1 to 14
- Oral fluconazole 800mg/day from Day 15 to Week 10
- Oral fluconazole 200mg/day thereafter

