11.5 Secondary Endpoints

Key Secondary Endpoint

DOOR as ordinal ranked maximum score tested by Win Ratio.

- 18-week Survival with CSF sterility by 2-weeks
- 18-week survival with CSF culture positivity beyond 2 weeks
- Grade 3 hematological adverse event by 2 weeks
- Grade 4 hematological adverse event by 2 weeks
- Lost to follow up before 18-weeks
- Serious Adverse Event through 18 weeks (e.g. all-cause re-hospitalization, permanent neurologic deficit)
- Death by 18-weeks

Secondary Endpoints

- 1) CSF culture sterility cumulative incidence over 18 weeks using Gray's method. All persons who are non-sterile at baseline will be included with all CSF culture data considered.
 - a) CSF culture sterility at 2 weeks, 6 weeks, 10, and 18 weeks will be summarized. All persons who are non-sterile at baseline will be included with all CSF culture data considered through the relevant study visit window.
- 2) 18-week survival time

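### Section 11.2 sets the primary analysis of DOOR at the last patient's week 2, although apart from death no DOOR rank is final before week 18

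*Combined protocol and SAP*

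**What the plan says.** Section 11.2 plans two analyses. On the first: "The primary analysis of the primary and key secondary endpoints will be conducted once the last patient completes 2 weeks of the study", or stops early. On the second: "A follow-up analysis will be conducted including all data through Week 18 once the last patient completes 18 weeks on study", again allowing for early discontinuation. Only the first is called primary.

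The synopsis, section 3.2 and section 11.5 each list one key secondary endpoint, a seven-level DOOR (a best, g worst) tested by Win Ratio. Levels a and b require survival to week 18 and differ in whether the CSF was sterile by week 2. Levels c and d are Grade 3 and Grade 4 hematological events in the first two weeks. Level e is loss to follow-up before week 18. Level f is "Serious Adverse Event through 18 weeks (e.g. all-cause re-hospitalization, permanent neurologic deficit"). Level g is death by week 18.

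On the comparator, section 4.1 says "The control group will consist of historical participants in the AMBITION trial". The synopsis estimates the time to complete enrolment as "Up to 12 months".

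**The concern.** The week-2 timing suits EFA, which is measured over about two weeks. It does not suit DOOR. Nothing in the document defines a two-week DOOR or says how to rank a participant with less than 18 weeks of follow-up.

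Run as written, the analysis labelled primary for DOOR has two options for late enrollees who are alive and in follow-up. It can leave them out, which conflicts with the intention-to-treat principle in 11.1. Or it can give them a provisional rank. From a, b, c or d, a provisional rank can only worsen to e, f or g by week 18. Such worsening is to be expected, since section 2.2 puts about half of the mortality after the first two weeks.

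The shortened follow-up affects only the low-dose cohort, because the controls are historical. If the controls are ranked on full follow-up, provisional ranks would flatter the low-dose regimen.

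A secondary point concerns the data behind level f. Its window is 18 weeks, but the recording rules stop earlier and disagree. Section 9.6 gives 2 weeks for Grade 3-5 clinical AEs and 9.7 gives 10 weeks for all AEs. The AE row in 7.1 appears to end at week 6, although its columns are uncertain in the extracted text. Sections 7.5, 8.1.1.2 and 9.4 suggest that AEs are still sought and documented up to termination at week 18. The wording needs reconciling, but late SAEs are not necessarily lost.

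**Working it through.** The plan gives no figure of its own for this point, so there is none to reproduce.

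**Step 1: which ranks are final at week 2.** The maximum score is read as the worst level reached.

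| State at week 2 | Ranks still possible at week 18 |
|---|---|
| Alive, no ranked event | a or b (by sterility), e, f, g |
| Grade 3 hematological event | c, e, f, g |
| Grade 4 hematological event | d, e, f, g |
| Lost but traceable | e, f, g |
| SAE | f, g |
| Dead | g |

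Only death is final.

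**Step 2: share short of 18 weeks at the cut.**
- Inputs: accrual of 52 weeks (the synopsis maximum of 12 months), assumed uniform; cut exactly 2 weeks after the last enrolment; N up to 50 (synopsis and 5.1).
- At that cut, a participant has 18 weeks only if enrolled at least 18 − 2 = 16 weeks before the last one.
- Short: 16/52 = 30.8%, and 0.308 × 50 = 15.4 participants.
- Complete: 36/52 = 69.2%.
- With the ±1 week window at the week-18 visit, the short share runs from 15/52 = 28.8% to 17/52 = 32.7%.

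**Step 3: remove those already dead, who do have a final rank.** The lower bound is the pooled 8.1% in Table 2.2, which is headed "The 2-week mortality of Ugandans on Amphotericin + Flucytosine with GCS=15". The higher values come from section 2.2: "10-week mortality rates between 24% and 37%, even under optimal research conditions". Late enrollees have 2 to 18 weeks of follow-up at the cut, so using these figures as the range of deaths by then is an assumption.

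| Assumed dead by the cut | Alive without a final rank | Of 50 |
|---|---|---|
| 8.1% | 30.8% × 0.919 = 28.3% | 14.1 |
| 24% | 30.8% × 0.76 = 23.4% | 11.7 |
| 37% | 30.8% × 0.63 = 19.4% | 9.7 |

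Participants already lost are not subtracted, because the document gives no loss rate.

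**Step 4: sensitivity.**
- Lock 4 weeks later (assumed), using data up to the lock: 12/52 = 23.1% short (11.5 of 50). Net of 8.1% to 37% dead, 21.2% to 14.5% (10.6 to 7.3 of 50).
- Accrual in 26 weeks (assumed): 16/26 = 61.5% short before deaths (30.8 of 50). Faster accrual makes the problem larger.
- Cut at the last patient's week 18: no participant lacks a rank because of the cut.

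**The case against.** The strongest reply is that this is mainly a matter of labelling. Section 11.2 already plans the week-18 analysis, so the complete DOOR will be produced without new data, visits or locks. Section 11.1 describes the analysis as descriptive, "with hypothesis testing performed for the primary efficacy endpoint", and 11.7 calls the secondary endpoints primarily descriptive. This stands and limits the consequence. It does not remove the error: 11.5 has DOOR tested by Win Ratio, and when two DOOR results exist the pre-specified label decides which one is definitive.

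The direction of bias can also be questioned. The document does not say how long the AMBITION controls were followed, and the survival comparison named in 4.1 is at 10 weeks. If control follow-up is shorter than 18 weeks, even a week-18 DOOR could be unbalanced. This is fair: the direction given above holds only if the controls are ranked on full follow-up.

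The rank table also has exceptions. The plan does not define the maximum score, although levels a and b need 18-week survival on any reading. A participant who fully withdraws consent may be fixed early, since 5.6 rules out further contact after withdrawal at Mulago. Neither changes the conclusion for participants alive and in follow-up.

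Finally, 11.3 leaves the details of historical-control comparisons to a Statistical Analysis Plan. That could supply ranking rules, but it does not defer the timing, which 11.2 fixes.

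**Conclusion.** The concern holds. The analysis that 11.2 labels primary for DOOR takes place before a material share of the low-dose cohort can be ranked. That share is about 19% to 28% (10 to 14 of 50) with uniform accrual over 52 weeks, a cut two weeks after the last enrolment, and 8% to 37% already dead. A 4-week lock delay would reduce it to about 15% to 21% (7 to 11 of 50). These sizes are illustrative, but the mismatch between timing and endpoint does not depend on them.

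It should be fixed. It does not threaten the trial's main result, because EFA is properly timed and the complete DOOR can be produced at an analysis already planned.

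**What to change.** - In 11.2, keep EFA and the 2-week safety endpoints at the week-2 lock, and name the planned week-18 lock as the primary analysis of DOOR.
- Reconcile 7.1, 9.6 and 9.7 so that SAEs for level f are recorded on the CRF at the existing contacts through week 18. The deadlines in 7.4, 9.5 and 9.11 can stay as reporting rules.
- State the SAE window available for the AMBITION controls, and sensibly also their survival and loss-to-follow-up windows, so that both groups can be ranked over the same period.

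The cost is one sentence in 11.2, wording in three other sections and a statement about the controls. No visits are added and EFA timing does not change. The primary DOOR result comes about 16 weeks later (18 − 2).

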11.3 Statistical Hypothesis

We hypothesize that a regimen with lower-dose 5-FC will be well tolerated, have reduced toxicity compared to a regimen with standard dose 5-FC, will have a superior rate of CSF fungal clearance compared to historical fluconazole monotherapy, and will have a statistically non-inferior rate of CSF fungal clearance compared to the historical standard-dose 5-FC. Full details of statistical considerations for making comparisons with historical controls will be provided in Statistical Analysis Plan.

11.4 Primary Endpoint:

The primary endpoint is CSF early fungicidal activity (EFA) during induction treatment: as measured in the change in \log_{10} CFU/mL of CSF/day and as assessed with general linear models. EFA from the low-dose 5-FC group will be compared to historical controls of standard-dose IV amphotericin + standard dose flucytosine and fluconazole.

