[figure not shown]
Induction Regimen	EFA	± SD	N	Ref
Single-dose Amphotericin + 5FC + fluconazole (1200 mg/day)	0.40	0.13	407	⁴³
Amphotericin	0.31	0.15	99	
Amphotericin + 5FC	0.42	0.10	100	³⁰
Amphotericin + fluconazole (800 mg/day)	0.32	0.10	99	
Amphotericin + 5FC	0.41	0.22	21	
Amphotericin + fluconazole (800 mg/day)	0.38	0.18	22	⁴⁴
Amphotericin + fluconazole (1200 mg/day)	0.41	0.35	23	
Amphotericin + voriconazole	0.44	0.20	13	
Amphotericin (5 days) + fluconazole (1200 mg/day)	0.30	0.11	30	⁴²
Amphotericin + 5FC	0.49	NA	30	⁴⁵
Amphotericin + 5FC + INF- β	0.64	NA	60	
Amphotericin (7 days) + fluconazole (1200 mg/day)	0.38	0.20	19	⁴⁶
Amphotericin (7 days) + fluconazole (1200 mg/day) + 5FC	0.50	0.15	18	
Fluconazole (1200 mg/day)	0.18	0.11	30	¹⁹
Fluconazole (800 mg/day)	0.07	0.17	30	
Amphotericin (1 mg/kg/day)	0.48	0.28	49	²⁶
Fluconazole (400 mg/day)	0.02	0.05	5	
Amphotericin + fluconazole (800 mg/day)	0.36	0.25	223	²⁵
Amphotericin + fluconazole (800 mg/day) + sertraline	0.43	0.39	128	²¹
Fluconazole (1200mg/day)	0.11	0.09	20	⁴⁷
Fluconazole (1200mg/day) + flucytosine	0.28	0.17	21	
Amphotericin 1 week (either 5FC or fluconazole)	0.40	0.24	179	
Amphotericin 2 week (either 5FC or fluconazole)	0.42	0.25	182	
Fluconazole (1200mg/day) + flucytosine	0.26	0.18	182	²
Amphotericin + 5FC	0.46	0.25	186	
Amphotericin + fluconazole (1200mg/day)	0.36	0.23	175	

Similarly, a separately published analysis found a correlation between EFA and 10-week mortality ($P=0.04$) using a larger collection of studies (Figure 2.5.B).⁴⁸ This analysis used the reported EFA from the publication, which differed slightly across publications and did not have primary data, thus was unable to account for differing demographics across highly diverse HIV-positive and HIV-negative cohorts. The included studies came from: the US, Canada, India, Thailand, Indonesia, Laos, Vietnam, Uganda, South Africa, Malawi, Botswana, Zimbabwe and Netherlands. This analysis only included randomized trials, and excluded two fluconazole monotherapy studies,^{19,26} which had poor EFAs $<0.20 \log_{10}$ CFU/ml/day and high mortality on the basis that these are clearly inferior therapies. This exclusion misses the point that EFA is a quantitative marker of microbiologic activity in humans.

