The control cohort will be drawn from the AMBITION trial that was conducted partly in Uganda.⁴³ This was a randomized clinical trial that evaluated single high-dose amphotericin B (10 mg/kg) with fluconazole (1200 mg/day) and flucytosine (100 mg/kg/day) for 2-week induction therapy of cryptococcal meningitis compared to standard amphotericin deoxycholate (1 mg/kg/day) with flucytosine (100 mg/kg/day). The trial enrolled participants who were HIV positive with a first episode of cryptococcal meningitis diagnosed by cryptococcal antigen or India ink staining. Participants were excluded if they were pregnant, had already taken amphotericin or fluconazole for >48 hours, had a previous serious reaction to the study medications or were taking a medication that would be contraindicated with the study medications. In Uganda, the trial enrolled 163 participants in the control arm and 164 in the intervention arm for a total enrollment of 327 Ugandan participants. The control cohort will be drawn from Ugandan participants. If IV liposomal amphotericin B is used in the investigational cohort then they will be drawn from the intervention arm. If IV deoxycholate amphotericin B is used in the investigational cohort then they will be drawn from the control arm. We will compare the EFA of all the control participants to the interventional participants using multivariate mixed linear regression, adjusting for confounding factors such as CD4+ count, GCS<15 or not, prior exposure to ART or not and other important clinical factors. We will also compare 10-week survival in the

interventional and control cohorts, using multivariate Cox regression, adjusting for the same clinical factors as the mixed regression model.

This 2018 and 2022 WHO recommended regimen is based on a phase III randomized clinical trial demonstrating that:

- i) 1 week of IV AMB had equivalent survival as 2 weeks of IV AMB;²
- ii) 1 week of IV AMB combination therapy was less toxic than 2 weeks of IV AMB;² and
- iii) Adjunctive flucytosine had superior survival to adjunctive fluconazole.²

A DSMB review by the full committee will occur after 10 participants have been enrolled with >2 weeks of accrued data. A local Ugandan community member will be invited to attend open DSMB meetings. The DSMB safety reports will be submitted to the IRBs and regulatory authorities.

Timing of ART Initiation or Switch.

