11.4.1 Sample Size & Statistical Power

Similar to phase II TB trials, rate of CSF yeast clearance has been used in moderate size phase II cryptococcal trials to demonstrate microbiologic efficacy as proof of concept. When the EFA is better than 0.20 CFU/mL/day, there is reasonably good survival after cryptococcal meningitis (Figure 2.5). Once the EFA is better than approximately 0.30 \log_{10} CFU/mL/day, there is less obvious incremental gains in survival beyond this threshold.⁶¹

Overall, the EFA is a quantitative measure of microbiologic activity in humans of an antifungal regimen.

For the EFA on a lower-dose 5-FC, we will have 36 participants with adequate data to calculate the EFA (i.e. non-sterile CSF culture at baseline and at least 1 follow up LP) and a standard deviation of approximately 0.20.

The CSF EFA will be interpreted in the context of other antifungal regimens published EFAs and the concurrent controls (Table 2.5). For example, if the lower-dose 5-FC arm has an EFA >0.30 \log_{10} CFU/mL/day and standard deviation of ± 0.20 , then the low dose 5-FC regimen will establish superiority compared to fluconazole 1200 mg regimen and non-inferiority with the all oral 5FC + fluconazole regimen. For a low-dose 5-FC arm EFA of 0.35, non-inferiority compared to the concurrent controls will be established with a margin of 0.17. For an EFA better than $0.30 \log_{10}$ CFU/mL/day, survival is relatively similar across antifungal regimens, as per section 2.5 and Figure 2.5.

A subsequent statistical analysis of the ASTRO clinical trial has demonstrated that 30 to 40 patients with EFA is sufficient to determine a significant difference in EFA. This was based on a bootstrap analysis of the participants of the ASTRO trial that is documented in table 11.4.1 below.

Table 11.4.1: EFA Calculated with the ASTRO Study (n=378)

Replicate Size	500 Bootstrap EFAs from randomly selected replicates
N	Mean (95%CI)
10	-0.454 (-0.768, -0.219)
15	-0.450 (-0.688, -0.257)
20	-0.449 (-0.664, -0.269)
30	-0.445 (-0.608, -0.292)
40	-0.445 (-0.593, -0.308)
50	-0.446 (-0.569, -0.316)
378 Actual	-0.444 (-0.489, -0.399)

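### Sections 4.1 and 11.4 name different models for the primary EFA comparison, and neither lets the variance differ between 36 trial participants and a much larger historical control group

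*Combined protocol and SAP*

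**What the plan says.** Section 11.4 states that EFA will be "as assessed with general linear models" and compared with historical controls. Section 4.1 describes that comparison differently, setting all controls against the "interventional participants using multivariate mixed linear regression, adjusting for confounding factors such as CD4+ count" and other clinical factors. Neither section states a variance structure. Section 11.3 adds: "Full details of statistical considerations for making comparisons with historical controls will be provided in Statistical Analysis Plan". Section 11.1, which bears that title, fixes the level ("all statistical testing will be two-sided and will be performed using a significance (alpha) level of 0.05") but does not mention variance either.

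The group sizes and spreads come from separate places:

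- Section 11.4.1 plans on the new cohort as follows: "we will have 36 participants with adequate data to calculate the EFA", "and a standard deviation of approximately 0.20".
- Section 4.1 says of AMBITION in Uganda that "the trial enrolled 163 participants in the control arm and 164 in the intervention arm". Controls come from whichever arm used the same amphotericin formulation.
- Table 2.5 lists "Single-dose Amphotericin + 5FC + fluconazole (1200 mg/day") with EFA 0.40, SD 0.13 and N=407. Its amphotericin + 5FC rows with an SD range from 0.10 to 0.25.

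The synopsis says that controls will be selected with weighting on eligibility, baseline characteristics and treatment received.

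**The concern.** A general linear model fitted in the usual way has one residual variance. A mixed model fitted in the usual way has one random-slope variance and one residual variance shared by both groups. When one group is four or more times the size of the other, the larger group largely determines that shared variance, while the smaller group's own variance largely determines the true uncertainty of the difference. If the small cohort is more variable than the controls, the interval is too narrow; if it is less variable, the interval is too wide.

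The cohorts come from different trials, so randomisation gives no reason to expect equal spread. Non-inferiority of fungal clearance is the trial's main objective (section 3.1.1). An interval that is too narrow would let a regimen whose true EFA lies at the margin be declared non-inferior more often than the stated level allows.

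**Working it through.** **The plan's own figures.** Section 11.4.1 gives n=36, SD about 0.20 and a margin of 0.17 at an observed EFA of 0.35. With these it states no control mean, control SD, control n, power or interval width. There is therefore no planned standard error to reproduce, and what follows compares two ways of computing one.

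**Inputs.** Cohort: n₁=36, s₁=0.20 (section 11.4.1). Controls: n₂=164, the Ugandan AMBITION intervention arm (section 4.1). Section 5.1 expects 10 to 15% of participants to be culture-negative and so to have no EFA. Applying that share to the controls is an assumption; it leaves 164 × 0.85 = 139 to 164 × 0.90 = 148. Control SD: s₂=0.13 (Table 2.5), varied below.

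**Formulas**, treating each participant's EFA as one observation:

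- Pooled: sₚ = √{[(n₁−1)s₁² + (n₂−1)s₂²]/(n₁+n₂−2)}; SE = sₚ√(1/n₁ + 1/n₂).
- Unpooled (Welch): SE = √(s₁²/n₁ + s₂²/n₂).
- One-sided error of the pooled 95% interval at the margin ≈ 1 − Φ(t × pooled SE / unpooled SE), with t on n₁+n₂−2 degrees of freedom.

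**Main illustration.**

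- sₚ = √[(35 × 0.04 + 163 × 0.0169)/198] = 0.1449.
- Pooled SE = 0.1449 × √(1/36 + 1/164) = 0.0267.
- Unpooled SE = √(0.04/36 + 0.0169/164) = 0.0348.
- Shortfall = 1 − 0.0267/0.0348 = 23%.
- One-sided error ≈ 1 − Φ(1.972 × 0.0267/0.0348) = 6.6%.

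A simulation of 40,000 trials with a true deficit of 0.17 gave 6.6% for the pooled interval and 2.5% for Welch.

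**Sensitivity**, with the cohort at SD 0.20, n=36:

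| Control SD | Control n | Pooled SE | Unpooled SE | Pooled/unpooled | One-sided error, pooled |
|---|---|---|---|---|---|
| 0.10 | 164 | 0.0228 | 0.0342 | 0.67 | 9.5% |
| 0.13 | 164 | 0.0267 | 0.0348 | 0.77 | 6.6% |
| 0.13 | 148 | 0.0271 | 0.0350 | 0.78 | 6.3% |
| 0.13 | 139 | 0.0275 | 0.0351 | 0.78 | 6.1% |
| 0.13 | 36 | 0.0398 | 0.0398 | 1.00 | 2.3% |
| 0.20 | 164 | 0.0368 | 0.0368 | 1.00 | 2.4% |
| 0.22 | 164 | 0.0399 | 0.0375 | 1.06 | 1.8% |
| 0.25 | 164 | 0.0445 | 0.0386 | 1.15 | 1.2% |

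The control SDs 0.10, 0.22 and 0.25 are those of other amphotericin + 5FC rows in Table 2.5 (N=100, 21 and 186).

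**Effect on the worked example.** Take an EFA of 0.35 against the 0.40 in Table 2.5, with 164 controls at SD 0.13. The difference is −0.05. The 95% half-width is 0.0526 pooled and 0.0703 with Welch, so the lower limits are −0.103 and −0.120. Both lie inside −0.17.

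**The case against.** A reader might infer that the plan uses an equal-variance model and that its interval is therefore about 23% too narrow. The documents do not support that, for these reasons:

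- No section states that variances are equal. Pooling is the default of the named methods, not a declared choice, and section 11.3 defers the details of the historical comparison.
- The pair SD 0.13 and n=164 is assembled. The SD is reported for N=407, and 164 is Ugandan enrolment. No Ugandan SD, no count of EFA-evaluable controls and no SD for the deoxycholate arm is given. Weighting would make the effective control number smaller still.
- The 0.20 is a rounded planning value. Setting it beside a published 0.13 is not evidence that low-dose participants will vary more.
- Within Table 2.5 the effect can vanish or reverse, so an interval that is too narrow is one possibility and not a prediction.
- The two-sample formula is not the standard error of a covariate-adjusted mixed model.

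All of this stands, and it makes the figures conditional. A more alarming figure is also available. The bootstrap intervals in Table 11.4.1 imply an SD near 0.44, for example (0.608 − 0.292)/(2 × 1.96) × √30 = 0.44. Set against 0.13, that gives an error of 14%. But this assigns one trial's spread to the new cohort alone and leaves the controls at 0.13, which nothing in the documents justifies.

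What the objection does not remove is that two different models are named, neither provides for unequal variance, and the group sizes make the result depend on it. The deferral does not settle the matter, because the statistical text available here is silent on it.

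**Conclusion.** The point holds as a weakness in how the primary comparison is specified, not as a demonstrated error in a reported figure. If the model is fitted with a common variance, the one-sided error in the illustrations above runs from about 1.2% (control SD 0.25) to 6.6% (control SD 0.13, 164 controls), against a nominal 2.5%. It reaches 9.5% if the controls have the smallest amphotericin + 5FC SD in Table 2.5. The direction cannot be known from the documents.

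These sizes rest on a cohort SD of 0.20, independent participant-level EFAs, unweighted controls and no covariate adjustment. With equal spread or equal group sizes the problem essentially disappears. The worked example's conclusion is unchanged with a control EFA of 0.40 and SD of 0.13. The exposure is for results near the margin.

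**What to change.** Name one primary model, in the same words, in sections 4.1 and 11.4, and state that it does not assume equal variances between the cohorts:

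- If individual EFAs are the outcome, use Welch or heteroscedasticity-consistent (HC3) standard errors, and robust errors if the controls are weighted.
- If serial cultures are modelled in a mixed regression, fit cohort-specific random-slope and residual variances.

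This costs about one sentence in each section. The interval may be slightly wider: with both SDs at 0.20, 36 participants and 164 controls, the 95% half-width goes from 0.0726 to 0.0739. In the main illustration, power with the unpooled standard error 0.0348 and margin 0.17 is Φ[(0.17 − d)/0.0348 − 1.96]. That is about 99.8% at a true deficit d of 0 and 93% at d = 0.05, so on these inputs no change in sample size is needed for this reason.
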